4.5. Duration of Participant Participation

Each participant will participate in the study for approximately 6 to 12 months for Stage 1 (nonpregnant women) and up to 16 months for Stages 2 and 3 (pregnant women and their infant participants). Stage 1 participants (nonpregnant women) willing and eligible to participate will return to receive a booster dose of GBS6 approximately 2 years after the primary dose of investigational product and will participate for additional visits through approximately 12 months.

4.6. Duration of Study

The study duration will be approximately 60 months.

4.7. Number of Participants

Refer to Table 2 below for a detailed description of the number of participants per stage and dose/formulation group. Participants who withdraw or are withdrawn from the study after randomization will not be replaced, regardless of the reason for withdrawal. A total of approximately 642 participants (66 nonpregnant women and 576 maternal participants and their infant participants) will be enrolled in this study by central randomization.

4.7.1. Stage 1

Approximately 66 participants (nonpregnant women) will be enrolled into Stage 1, 22 participants at each formulation of GBS6 (with/without AlPO4) and 22 participants in the placebo group. Stage 1 participants (nonpregnant women) will receive a booster dose of GBS6 (20 µg CPS/serotype/dose with AlPO4) approximately 2 years after initial investigational product administration.

4.7.2. Stage 2

Approximately 360 maternal participants will be enrolled into Stage 2. The first 42 participants within a dose level (low, middle, high) will compose the sentinel cohort with 14 participants at each dose/formulation and 14 participants in the placebo group. The enrollment rate in each of the sentinel cohorts will be limited to a maximum of 5 participants per day. Further enrollment will be expanded at each dose level until 78 additional participants are enrolled (expanded cohort).

4.7.3. Stage 3

Approximately 216 maternal participants will be enrolled into Stage 3 (approximately 162 from South Africa/UK and 54 from the US), 108 at the selected GBS6 dose/formulation and 108 in the placebo group. Enrollment will be monitored to help ensure distribution of vaccination across the gestational age range of ≥24 0/7 to ≤35 6/7 weeks.

Stage 1 Dose/Formulation Group^a Total (1:1:1)GBS6 (20 µg CPS/serotype/dose) with AlPO4 22 Highest Doseb GBS6 (20 µg CPS/serotype/dose) without AIPO4 22 22 Placebo (saline control) Expanded Stage 2 Dose/Formulation Groups Sentinel Total (1:1:1)(1:1:1)GBS6 lowest dose with AlPO4 14 26 40 Dose GBS6 lowest dose without AlPO4 14 26 40 Placebo (saline control) 14 26 40° Middle GBS6 middle dose with AlPO4 14 26 40 Dose GBS6 middle dose without A1PO4 14 26 40 Placebo (saline control) 14 26 40° GBS6 highest dose with AlPO4 14 26 40 Highest Dose GBS6 highest dose without AlPO4 14 26 40 14 26 40° Placebo (saline control)

Total (1:1)

108

108

Table 2. Planned Participants: Total and Number in Each Stage and Group

Abbreviations: AIPO₄ = aluminum phosphate; CPS = capsular polysaccharide; FIH = first-in-human.

- a. Stage 1 participants (nonpregnant women) willing and eligible to participate will return to receive a booster dose of GBS6 (20 μg CPS/serotype/dose with AlPO₄) approximately 2 years after the primary dose of investigational product.
- b. One hundred four healthy adults (males and females) 18 to 49 years of age have received this dose level (~52/formulation with/without AlPO₄) in the US FIH Phase 1/2 study (C1091001).
- c. Approximately 120 pregnant control participants receiving placebo (saline control) in total in Stage 2.

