10.1. Sample Size Determination

This is a Phase 1/2 randomized, placebo-controlled, observer-blinded study to assess safety, tolerability, and immunogenicity of GBS6 in healthy nonpregnant as well as pregnant women and their infant participants. The study consists of 3 stages. The sample sizes at each stage are not driven by any specific hypothesis testing.

Approximately 66 nonpregnant women will be enrolled at Stage 1, 22 participants per group to receive placebo (saline control) or GBS6 (20 µg CPS/serotype/dose) with or without AlPO4. Participants in Stage 1 will also receive a booster dose of GBS6 (20 µg CPS/serotype/dose with AlPO4) approximately 2 years after the initial dose of investigational product. Sample size for the participants receiving GBS6 booster dose is dependent upon the number of participants providing consent to continue in the study.

Approximately 360 pregnant women will be enrolled at Stage 2, 40 participants at each GBS6 dose/formulation and a total of 120 participants in the placebo group. Refer to Table 2 for a detailed description of the number of participants per group. Approximately 216 pregnant women will be enrolled at Stage 3 (approximately 162 from South Africa/UK and 54 from the US), 108 participants at the selected GBS6 dose/formulation and 108 participants in the placebo group. Enrollment will be monitored to help ensure distribution of vaccination across the gestational age range of >24 0/7 to <35 6/7 weeks.

Table 9 shows the probability of observing at least 1 AE for a given true event rate of a particular AE, for various sample sizes. For example, if the true AE rate is 10%, with 14 participants in each dose/formulation group, there is 77% probability of observing at least 1 AE.

Table 9. Probability of Observing at Least 1 AE by Assumed True Event Rates
With Different Sample Sizes

Sample Size		Assumed True Event Rate of an AE				
(N)	1.0%	2.0%	2.5%	3.0%	5.0%	10.0%
14	0.13	0.25	0.30	0.35	0.51	0.77
22	0.20	0.36	0.43	0.49	0.68	0.90
28	0.25	0.43	0.51	0.57	0.76	0.95
40	0.33	0.55	0.64	0.70	0.87	0.99
44	0.36	0.59	0.67	0.74	0.90	0.99
80	0.55	0.80	0.87	0.91	0.98	>0.99
120	0.70	0.91	0.95	0.97	>0.99	>0.99
240	0.91	0.99	>0.99	>0.99	>0.99	>0.99
348	0.97	>0.99	>0.99	>0.99	>0.99	>0.99

Abbreviations: AlPO₄ = aluminum phosphate; CPS = capsular polysaccharide.

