#### 3.6. Safety Endpoints

#### 3.6.1. Adverse Events

All AEs are collected on the case report form (CRF) for nonpregnant women (Stage 1), maternal participants (Stages 2 and 3), and infant participants (Stages 2 and 3) and will be categorized according to the current version (at the time of reporting) of MedDRA. For nonpregnant women (Stage 1), AEs will be collected following the primary and booster vaccinations separately.

An immediate AE is defined as any AE that occurred within the first 30 minutes after administration of the investigational product for nonpregnant women (Stage 1) and maternal participants (Stages 2 and 3) (see Section 8.8.2 [Immediate Adverse Events] of the protocol).

An MAE is defined as a nonserious AE that results in an evaluation at a medical facility. MAEs will be assessed from screening up to Visit 4 for nonpregnant women (Stage 1), from screening up to Visit 9 for maternal participants (Stages 2 and 3), and up to Visit 7 for infant participants (Stages 2 and 3). In addition, for participants receiving the booster vaccination in Stage 1, MAEs will be assessed from Visit 5 up to Visit 10.

AEs of special interest for infant participants (Stages 2 and 3) are major congenital anomalies, developmental delay, and suspected or confirmed GBS infection and are collected from birth through the end of the study (12-month postbirth visit). GBS infections that occurred during Days 1 through 7 are referred to as early-onset disease (EOD) and those that occurred during Days 8 through 90 are referred to as late-onset disease (LOD), where Day 1 is the day of birth.

AEs and SAEs will be captured and reported in accordance with Pfizer reporting standards and following the time period of collection outlined in Section 9.1.4 (Table 8) of the protocol.

A 3-tier approach will be used to summarize AEs. Under this approach, AEs are classified into 1 of 3 tiers. Different analyses may be performed for different tiers.

- Tier 1 events: These are prespecified events of clinical importance and, if any, are maintained in a list in the product's Safety Surveillance Review Plan. There are no preidentified Tier 1 events for this study.
- Tier 2 events: These are events that are not Tier 1 but are "common." A MedDRA
  preferred term is defined as a Tier 2 event if there are 4 or more participants in at least
  1 vaccine group.
- Tier 3 events: These are events that are neither Tier 1 nor Tier 2 events.

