#### 5.2. General Methods

Descriptive summary statistics will be provided for all endpoints. Unless otherwise explicitly stated, the descriptive statistics for continuous variables are: n, mean, median, standard deviation, minimum, and maximum. The descriptive statistics for categorical variables are: the proportion (%), n (the numerator), and N (the denominator) used in the proportion calculation.

The dose/formulation level and vaccine group (hereafter referred to as vaccine group) in this study are defined as below:

- GBS6 (5 μg)/AlPO4
- GBS6 (5 μg)/no AlPO4
- GBS6 (10 μg)/AlPO4
- GBS6 (10 μg)/no AlPO4
- GBS6 (20 μg)/AlPO4
- GBS6 (20 μg)/no AlPO4
- Placebo

All safety and immunogenicity summaries in each stage of the study will be presented by a subset or complete set dependent on the study stage. In Stage 1 for primary vaccination, the subset will only include Groups 5 through 7; Stage 1 for booster vaccination will only include GBS6 (20  $\mu$ g)/AlPO4; Stage 2 will include all vaccine groups; Stage 3 will only include GBS6 (20  $\mu$ g)/no AlPO4 and placebo. Unless otherwise explicitly stated, all Stage 2 maternal participants from both sentinel and expanded cohorts will be combined, by vaccine groups listed above. Similarly, all Stage 2 infant participants from both sentinel and expanded cohorts will be combined according to their mother's vaccine group.

Both safety and immunogenicity results will be summarized separately for nonpregnant women with primary vaccination (Stage 1), nonpregnant women with a booster vaccination (Stage 1), maternal participants in Stage 2, maternal participants in Stage 3, infant participants in Stage 2, and infant participants in Stage 3. Immunogenicity data from Stage 3 will also be summarized separately by country (USA/UK, South Africa).

The GBS6 IgG antibody levels will be standardized as current quantitated values × correction factor. The lower limit of quantitation (LLOQ) values will be standardized as LLOQ = LLOQ × correction factor. The correction factors are set as follows: Ia, 0.46628125; Ib, 0.463392157; II, 1.451696809; III, 0.727236264; IV, 0.686258373; and V, 0.236850746. The standardized quantitated values will be reported for all analyses.

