#### 5.2.1.3. Safety Data

Similarly, the exact 2-sided 95% CIs using the Clopper and Pearson method will be provided by vaccine group for all primary safety endpoints, proportions of participants reporting local reactions, systemic events (Stage 1 nonpregnant women with primary vaccination [3 vaccine groups], Stage 1 nonpregnant women with booster vaccination [1 vaccine group], Stage 2 maternal participants [7 vaccine groups], and Stage 3 maternal participants [2 vaccine groups]), AEs, SAEs, and MAEs (Stage 1 nonpregnant women with primary vaccination

[3 vaccine groups], Stage 1 nonpregnant women with booster vaccination [1 vaccine group], Stage 2 maternal participants [7 vaccine groups], and Stage 3 maternal participants [2 vaccine groups] and their infants), obstetric complications, delivery outcomes, and delivery mode (Stages 2 and 3 maternal participants), and AEs of special interest (Stages 2 and 3 infant participants).

For Tier 2 AEs only, 95% CIs for the difference in proportions between each GBS6 vaccine group and placebo (risk difference) based on the Chan and Zhang method will be provided for nonpregnant women with primary vaccination (Stage 1), nonpregnant women with booster vaccination (Stage 1), maternal participants (Stages 2 and 3), and infant participants (Stages 2 and 3).

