# 6.1.2.4. Proportion of Maternal Participants Reporting AEs Through 1 Month After Administration of the Investigational Product

Endpoints: AEs experienced by maternal participants (Stages 2 and 3).

- Analysis time points: Day 1 to 1 month after vaccination.
- Analysis population: Safety population for maternal participants (Stages 2 and 3).
- Analysis methodology: Descriptive summary statistics.
- Supporting objective: Primary safety objective.

- Raw data: The number of participants with AEs (n), proportion, and associated 2-sided exact 95% CI will be presented for any AEs, SAEs, immediate AEs, severe AEs, related AEs, MAEs, and AEs leading to withdrawal, by vaccine group. Additionally, the number of participants with AEs (n), proportion, and associated 2-sided exact 95% CI will be presented for any AE, each SOC, and each preferred term within SOC, by vaccine group.
- Tier 2 AEs: The number of participants with AEs (n), proportion, risk difference, and associated 2-sided exact 95% CI will be presented for each preferred term.

Figures: None.

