## 6.7. Safety Summaries and Analyses

#### 6.7.1. Adverse Events

It should be recognized that most studies are not designed to reliably demonstrate a causal relationship between the use of an investigational product and an AE or group of AEs. Except for select events in unique situations, studies do not employ formal adjudication procedures for the purpose of event classification. As such, safety analysis is generally considered as an exploratory analysis and its purpose is to generate hypotheses for further investigation. The 3-tier approach facilitates this exploratory analysis. There will be no adjustment for multiple comparisons in the analyses.

AEs will be reported in accordance with the Pfizer reporting standards. For Tier 2 and Tier 3 events, the proportion of participants with AEs in each vaccine group will be presented. In addition, for Tier 2 AEs, 2-sided 95% CIs for the difference in observed proportions between each vaccine group and the placebo will be constructed. Tier 3 events will be summarized as part of the overall AE summary.

AEs, MAEs, and SAEs occurring after signing the ICD and prior to vaccination will be summarized separately for nonpregnant women receiving the primary and booster vaccinations from Stage 1 and for maternal participants from Stages 2 and 3.

Listings of participants reporting any AE will be generated for all participants.

Additionally, immediate AEs will be generated for nonpregnant women receiving the primary and booster vaccinations from Stage 1 and for maternal participants from Stages 2 and 3.

All summaries and listings for the AEs will be generated separately for nonpregnant women receiving the primary and booster vaccinations (Stage 1), maternal participants (Stages 2 and 3), and infant participants (Stages 2 and 3). Additionally, suspected or confirmed GBS infections for infant participants (Stages 2 and 3) will be summarized by EOD and LOD as defined in Section 3.6.1.

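### In Stage 2 the fixed four-case rule for Tier 2 adverse events is a 10% bar in each GBS6 group but 3.3% on pooled placebo, so with no vaccine effect the displayed risk differences for uncommon terms lean towards the vaccine

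*Protocol*

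**What the plan says.** Protocol 10.1 plans for Stage 2 "40 participants at each GBS6 dose/formulation and a total of 120 participants in the placebo group". The note to protocol Table 2 confirms that placebo is counted across the three dose levels: "Approximately 120 pregnant control participants receiving placebo (saline control) in total in Stage 2".

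SAP 5.2 has a single placebo entry in its list of vaccine groups and adds: "Unless otherwise explicitly stated, all Stage 2 maternal participants from both sentinel and expanded cohorts will be combined, by vaccine groups listed above". SAP 5.2.1.3 accordingly refers to "Stage 2 maternal participants [7 vaccine groups". The groups compared are therefore six of 40 and one of about 120.

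SAP 3.6.1 sets the threshold: a "preferred term is defined as a Tier 2 event if there are 4 or more participants in at least" one vaccine group. It is a raw count with no reference to group size. SAP 5.2.1.3 then states: "For Tier 2 AEs only, 95% CIs for the difference in proportions between each GBS6 vaccine group and placebo (risk difference", by the Chan and Zhang method. SAP 6.1.2.4 applies this to mothers through 1 month, and SAP 6.1.3.2 applies it to infants from birth to 6 weeks by maternal group.

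Terms below the threshold still appear. For mothers through 1 month, SAP 6.1.2.4 has the number, proportion and exact 95% CI "presented for any AE, each SOC, and each preferred term within SOC, by vaccine group". SAP 6.1.3.2 does the same for infants.

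**The concern.** A fixed count is a neutral filter only when the groups are of equal size. Here the comparator is three times as large as each vaccine group, so for an uncommon term the likeliest reason to enter the Tier 2 table is a chance-high placebo count. That same count is then subtracted in all six risk differences. Selecting on the quantity being subtracted pushes the displayed differences below zero even when the vaccine does nothing.

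In the readable text, the Tier 2 risk differences are the only between-group safety estimates planned. A reader going down that table would see a run of small negative differences among the uncommon terms and could take them as reassurance. Meanwhile a pattern spread thinly over the vaccine groups and absent on placebo could receive no risk difference at all.

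**Working it through.** **Inputs.** Six GBS6 groups of 40 and placebo of 120 (protocol Table 2 and 10.1). Threshold of 4 in any one group (SAP 3.6.1). Risk differences for Tier 2 only (SAP 5.2.1.3). The documents give no true rate for any preferred term, so the rate r is an assumption, taken from 0.5% to 10%. Protocol Table 9 itself uses 1% to 10%.

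**The plan's own figures.** 6 × 40 + 120 = 360, the stated Stage 2 total. Table 9 is 1 − (1 − p)^N: N = 14 at 10% gives 0.771 (stated 0.77), N = 40 at 3% gives 0.704 (0.70), N = 120 at 1% gives 0.701 (0.70). These reproduce.

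**The bar.** 4/40 = 10.0%; 4/120 = 3.3%.

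**Selection with no vaccine effect.** Let X be the count in one GBS6 group, Bin(40, r), and Y the placebo count, Bin(120, r). Write a = P(X ≥ 4) and b = P(Y ≥ 4).

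- P(some GBS6 group triggers) = 1 − (1 − a)^6
- P(selected) = S = 1 − (1 − a)^6 (1 − b)
- Share triggered by placebo alone = b(1 − a)^6 / S
- Mean placebo rate given selection = [120r − E(Y; Y ≤ 3)(1 − a)^6] / (120 S)
- Mean GBS6 rate given selection = [40r − E(X; X ≤ 3)(1 − a)^5 (1 − b)] / (40 S)

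At r = 1%: a = 0.00069 and b = 0.0330, so S = 1 − 0.99589 × 0.96702 = 0.0370. The placebo-alone share is 0.0330 × 0.99589 / 0.0370 = 0.89. The mean placebo rate is (1.2 − 1.0590 × 0.99589) / (120 × 0.0370) = 3.28%. The mean GBS6 rate is (0.4 − 0.3972 × 0.99658 × 0.96702) / (40 × 0.0370) = 1.16%. The mean displayed difference is 1.16 − 3.28 = −2.1 points.

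| True rate | Any GBS6 group ≥ 4 | Placebo ≥ 4 | Selected | By placebo alone | Mean difference, points |
|---|---|---|---|---|---|
| 1% | 0.4% | 3.3% | 3.7% | 89% | −2.1 |
| 2% | 4.8% | 22% | 26% | 81% | −1.3 |
| 3% | 17% | 49% | 58% | 70% | −0.7 |
| 5% | 59% | 86% | 94% | 37% | −0.1 |
| 8% | 95% | 99% | >99% | 5% | 0.0 |

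At 0.5% the mean difference is −2.6 points, and at 4% it is −0.3. Having six GBS6 groups that can each trigger the rule does not offset the larger placebo group.

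**With a true effect.**

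- If the rate is doubled in all six GBS6 groups, the error in the displayed difference is between −0.4 and about 0 points for placebo rates of 0.5% to 5%.
- If it is tripled, the error runs from +0.8 down to 0.0, so the lean reverses.
- If only one group is affected (3% against 1% elsewhere), that group shows +4.2 against a true +2.0, while the other five average −1.1.

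**Examples.**

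- 3/40 in every GBS6 group (18/240) against 0/120: Fisher p = 0.001, no risk difference for any group.
- 0/40 against 4/120: Fisher p = 0.57, risk difference of −3.3 points displayed.

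**Alternative rules with no vaccine effect.**

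- Total of 4 or more over all seven groups: mean difference 0. Given the total, each woman is equally likely to be a case, whatever her group.
- Equal percentage bar (4/40 or 12/120): overcorrects, by +1.5, +1.4 and +1.2 points at 1%, 2% and 3%.

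**Detecting a one-group excess** (7.5% in one GBS6 group, 0.5% elsewhere): a risk difference is shown 35% of the time now, 68% with a total of 4, and 9% with a total of 8.

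**The case against.** The strongest reply is that this is a display rule in a descriptive study. SAP 5.1.2 uses no statistical decision rules, and SAP 6.7.1 calls the safety analysis exploratory. The protocol's stopping rules count GBS6 recipients only, and the two review committees see safety data separately. All of this stands: no planned decision depends on the Tier 2 table.

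A reader might infer that events confined to GBS6 disappear from the report. They do not. Every preferred term is printed by group with an exact interval. SAEs, MAEs, obstetric complications, delivery and birth outcomes, and infant events of special interest are reported by group without any tier filter.

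A reader might also infer that the safety tables as a whole favour the vaccine. That is not supported either. The lean is confined to uncommon terms, and few of the rarest are selected. Averaged over displayed terms it is only about −0.2 points if true rates are log-uniform from 0.2% to 20%, or uniform from 0.5% to 10%; both spreads are assumptions. It does not arise in Stage 1 primary vaccination (22 per group) or in Stage 3 (1:1), where the compared groups are equal.

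Finally, Stage 2 is no longer blinded. Protocol 2.2.5 cites results of the second and third interim analyses, and SAP 7.2 unblinds the study team to a stage at its interim analysis. Replacing the rule now would be a change made after unblinding, so an addition is preferable to a replacement.

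What survives is that the rule picks its displayed differences partly on the comparator's own count, in a direction that can be calculated, in tables meant to generate safety hypotheses.

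**Conclusion.** The point holds for Stage 2 mothers and their infants, as a bias in which risk differences are displayed. With no vaccine effect, the mean displayed difference is −2.1, −1.3 and −0.7 points at true rates of 1%, 2% and 3%, −0.1 at 5% and nil from 8%. Of terms at 1%, 2% and 3%, 3.7%, 26% and 58% are selected.

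This rests on the planned group sizes, on placebo being analysed as one group, on infant numbers close to maternal numbers, and on assumed term rates. The direction under no effect does not depend on a particular rate; the size does. Under a true excess in all GBS6 groups the lean shrinks or reverses, so the plan cannot be said to understate vaccine harm in general. What is lost is the difference and its interval for some terms, not the data. The correction is worth making because it is simple and loses nothing now shown.

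**What to change.** Add to SAP 3.6.1, for Stage 2 mothers and infants: besides the current Tier 2 terms, Chan-Zhang risk differences with 95% CIs will be given for every preferred term reported by 4 or more participants across all seven vaccine groups combined. Any term with 4 cases in one group also has 4 in total, so every term selected now is kept, and the full set has no lean when there is no vaccine effect. Label the table as an addition made after Stage 2 was unblinded, and flag the rows that met the four-in-one-group rule.

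The cost is one sentence, some programming and a much longer table: at a 1% rate about 49% of terms would get risk differences, against 4% now, each with six intervals. SAP 6.7.1 already says "There will be no adjustment for multiple comparisons in the analyses", and that caveat should stand beside the table.

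One gap remains: a term with only 3 cases in all, all in one GBS6 group, would still get no risk difference. A higher total, such as 8, should not be used to shorten the table, because it catches a one-group excess less often than the current rule (9% against 35% in the case worked above). An equal percentage bar should not be used either, since it leans the other way.
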